## 13.0 REGULATORY CONSIDERATIONS

### Good Clinical Practice

The study will be conducted in accordance with the International Conference on Harmonisation (ICH) for Good Clinical Practice (GCP) and the appropriate regulatory requirement(s). The investigator will be thoroughly familiar with the appropriate use of the drug as described in the protocol and Investigator's Brochure. Essential clinical documents will be maintained to demonstrate the validity of the study and the integrity of the data collected. Master files should be established at the beginning of the study, maintained for the duration of the study and retained according to the appropriate regulations. This is the responsibility of the sponsor-investigator.

### Ethical Considerations

The study will be conducted in accordance with ethical principles founded in the Declaration of Helsinki (see appendix). The IRB/IEC will review all appropriate study documentation in order to safeguard the rights, safety and well-being of the patients. The study will only be conducted at sites where IRB/IEC approval has been obtained. The protocol, Investigator's Brochure, informed consent, advertisements (if applicable), written information given to the patients (including diary cards), safety updates, annual progress reports, and any revisions to these documents will be provided to the IRB/IEC by the investigator. Novartis requests that the protocol and informed consent documents be reviewed by Novartis or designee prior to IRB/IEC submission.

### Patient Information and Informed Consent

The principles of informed consent are described by Federal Regulatory Guidelines (Federal Register Vol. 46, No. 17, January 27, 1981, part 50) and the Office for Protection from Research Risk Reports: Protection of Human Subjects (Code of Federal Regulations 45 CFR46). They must be followed to comply with FDA regulations for the conduct and monitoring of clinical investigations.

### Institutional Review

This study must be approved by an appropriate institutional review committee as defined by Federal Regulatory Guidelines (Ref. Federal Register Vol. 46, 17, January 27, 1981, part 56) and the Office for Protection from Research Risks Reports: Protection of Human Subjects (Code of Federal Regulations 45 CFR 46).

### Patient Confidentiality

In order to maintain patient privacy, all data capture records, drug accountability records, study reports and communications will identify the patient by initials and the assigned patient number. The investigator will grant monitor(s) and auditor(s) from Novartis or its designees and regulatory authority(ies) access to the patient's original medical records for verification of data gathered on the data capture records and to audit the data collection process. The patient's

confidentiality will be maintained and will not be made publicly available to the extent permitted by the applicable laws and regulations.

## **Data Management**

Electronic Case Report Forms (eCRFs) will be developed to include all necessary patient information, laboratory data, treatment data, and adverse event data. This data will be housed securely within the web-based ONCORE database and will be password protected. The ONCORE database is 21 CFR Part 11 compliant. The Database Manager at CCF will train the data entry designee(s) on the ONCORE system. Upon completion of the training and electronic signature certification, the Database Manager will create a user account in ONCORE for the data entry designee(s). The data entry designee(s) will proceed with entering the patient(s) relevant information and eCRF forms. The Database Manager will periodically run reports across all studies to ensure timely and accurate entry of accrual data.

## **Protocol Compliance**

The investigator will conduct the study in compliance with the protocol given approval/favorable opinion by the IRB/IEC and the appropriate regulatory authority(ies). Changes to the protocol will require approval from Novartis (changes are to be submitted by CCF) and written IRB/IEC approval/favorable opinion prior to implementation, except when the modification is needed to eliminate an immediate hazard(s) to patients. The IRB/IEC may provide, if applicable regulatory authority(ies) permit, expedited review and approval/favorable opinion for minor change(s) in ongoing studies that have the approval /favorable opinion of the IRB/IEC. The CCF Principal Investigator will submit all protocol modifications to Novartis and the regulatory authority(ies) in accordance with the governing regulations. All participating subsite(s) will contact the CCF study coordinator. Any departures from the protocol must be fully documented in the source documents.

## **On-site Audits**

Regulatory authorities, the IEC/IRB, and/or Novartis may request access to all source documents, data capture records, and other study documentation for on-site audit or inspection. Direct access to these documents must be guaranteed by the investigator, who must provide support at all times for these activities.

## **Drug Accountability**

Accountability for the drug at all study sites is the responsibility of the principal investigator. The investigator will ensure that the drug is used only in accordance with this protocol. Drug accountability records indicating the drug's delivery date to the site (if applicable), inventory at the site (if applicable), use by each patient, and return to Novartis or disposal of the drug (if applicable and if approved by Novartis) will be maintained by the clinical site. Accountability records will include drug receipt/destruction dates, quantities, lot numbers, expiration dates (if applicable), and corresponding registered patient numbers. All material containing eltrombopag will be treated and disposed of as hazardous waste in accordance with governing regulations.

### **Premature Closure of the Study**

This study may be prematurely terminated, if in the opinion of the investigator or Novartis, there is sufficient reasonable cause. Written notification documenting the reason for study termination will be provided to the investigator or Novartis by the terminating party.

Circumstances that may warrant termination include, but are not limited to:

1. Determination of unexpected, significant, or unacceptable risk to patients
2. Failure to enter patients at an acceptable rate
3. Insufficient adherence to protocol requirements
4. Insufficient complete and/or evaluable data
5. Plans to modify, suspend or discontinue the development of the drug
6. Should the study be closed prematurely, all study materials must be returned to Novartis

### **Record Retention**

The sponsor-investigator will maintain all study records according to applicable Cleveland Clinic Foundation regulatory requirement(s).

### **Patient Consent and Peer Judgment**

All institutional, NCI, FDA, state and Federal regulations concerning informed consent and peer judgment will be fulfilled.

#### **Appendix I: WHO Bleeding Scale**

	Modified Response Criteria
Grade 0	No bleeding
Grade 1	Petechiae
Grade 2	Mild blood loss
Grade 3	Gross blood loss
Grade 4	Debilitating blood loss

**Appendix II: ECOG Performance Status**

	Modified Response Criteria
PS 0	Fully active, able to carry on all pre-disease performance without restriction
PS 1	Restricted in physically strenuous activity but ambulatory and able to carry out work of a light or sedentary nature e.g. light house work, office work.
PS 2	Ambulatory and capable of all self-care but unable to carry out any work activities. Up and about more than 50% of waking hours.
PS 3	Capable of only limited self-care, confined to bed or chair more than 50% of waking hours.
PS 4	Completely disabled. Cannot carry on any self-care. Totally confined to bed or chair.

**Appendix III: AML IWG Response Criteria (Cheson, 2003)**

	Modified Response Criteria
Morphologic leukemia-free state	Bone marrow blasts <5% No extramedullary disease
Morphologic CR	Bone marrow blasts <5%; Neutrophils >1Gi/L; HI-P a b No extramedullary disease
Cytogenetic CR	As morphologic CR and normal cytogenetics No extramedullary disease
Molecular CR	As morphologic CR and no molecular mutations No extramedullary disease
Partial remission	Bone marrow blasts >50% or decrease to 5-25% (<5% if Auer rod positive) Neutrophils >1Gi/L; HI-P a b

Modification to Cheson 2003.

HI-P : Baseline <20Gi/L: >20 Gi/L and 2x baseline; Baseline  $\geq$ 20 Gi/L:  $\geq$ 50 Gi/L and 2x baseline

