In older patients inability to achieve CR, particularly as a result of delayed platelet recovery, can lead to prolonged dependence on platelet transfusions, risk of bleeding and most importantly, inability to proceed with post-remission therapy. Recent data from M. D. Anderson Cancer Center and the Southwest Oncology Group showed that patients achieving CR were more likely to be alive at 3, and particularly at 5 years than patients achieving partial complete remission (CRp) (relative risk for 5-year survival, 3.0; 95% CI, 1.0 to 9.0;  $P < .02$ ).(6) A multivariate analysis in the same cohort that adjusted for covariates including age at diagnosis, cytogenetics, prior chemotherapy, antecedent hematologic disorder (AHD), poor performance status, response (ie, CR, CRp) indicated that CR was independently associated with a longer relapse-free survival and OS relative to CRp. Leukemia patients not cured almost uniformly die from sequelae of being immunocompromised, thrombocytopenic, or both. It stands to reason that abrogation of periods of cytopenia following remission induction therapy could reduce complications, which in turn could lead to better outcomes for older adults.

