### **1.4 Rationale for using Eltrombopag in the Treatment of AML**

To date, there is no effective strategy for managing thrombocytopenia in AML patients following induction chemotherapy (IC) other than supportive platelet transfusions, which are limited by supply, cost and transfusion refractoriness. Eltrombopag is capable of enhancing megakaryopoiesis without stimulating leukemic blasts or activating platelets – properties that make it a candidate drug of choice for therapeutic intervention in the post-induction phase of

AML treatment. Early platelet count recovery following IC has significant clinical implications including decrease in thrombocytopenia-related bleeding complications, reduced necessity for platelet transfusions, improved complete remission rates and timely initiation of post-remission therapy - factors that present challenges particularly in the management of older patients.

While most of the eltrombopag studies in AML are in the relapsed or refractory setting or in those unable to withstand aggressive induction chemotherapy, a phase 1/2 study has been opened to assess the efficacy of eltrombopag in AML patients undergoing consolidation therapy following achievement of CR. We propose a novel therapeutic strategy where eltrombopag will be used in older AML patients undergoing IC who have no morphologic evidence of disease on a day 14 bone marrow assessment, with the goal of accelerating platelet recovery. We hypothesize that as eltrombopag acts at a TPO receptor site which is different from the native TPO binding site, it will accelerate megakaryopoiesis by acting synergistically with endogenous TPO, the levels of which have been shown to rise twenty-fold with drop in platelet counts below 50000/ $\mu$ L in AML patients while undergoing cytotoxic chemotherapy.(27) Our proposed use of eltrombopag in AML-associated thrombocytopenia thus represents a shift in treatment paradigm, with expected benefits in terms of decreased treatment-related morbidity, cost and potentially improved disease outcome. Currently, there are no competing trials in the public domain for this proposed study.

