### **2.2 Secondary Objectives**

221 To determine the effect of eltrombopag on megakaryopoiesis - median time to reach platelet count  $\geq 50,000 / \mu$ L and  $\geq 100,000 / \mu$ L, number of days of platelet transfusion, rates of platelet transfusion-independence and the median time to reach platelet transfusion-independence.

222 To determine the effect of eltrombopag on the rates of clinically significant bleeding events (CSBE) [Appendix I].

223 To determine the effect of eltrombopag on erythropoiesis the median time to red blood cell transfusion independence.

224 To determine the effect of eltrombopag on granulopoiesis- the time taken to reach an absolute neutrophil count of  $\geq 500 / \mu$ L.

225 To determine the safety and tolerability of eltrombopag in AML patients undergoing remission IC - incidence and severity of eltrombopag-related adverse events.

226 To determine the rates of CR, rates of CRp, time to attain CR, and time to initiation of postremission therapy.

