**3) Kinetics of erythrocytic recovery:** Parameters to be assessed will include the median number of days needed to reach a hemoglobin level  $> 8\text{ g/dl}$  (first of the 5 consecutive days with hemoglobin  $> 8\text{ g/dl}$ ) starting from the first day of study drug administration, maximal rise in hemoglobin level after achieving transfusion-independence and rates of red blood cell transfusion-independence within 4 weeks of IC. An erythroid response in patients with a pretreatment hemoglobin level of  $< 8\text{ g/dL}$  (transfusion-dependent) will be defined as an increase in the hemoglobin level by  $1.5\text{ g/dL}$  or more without transfusion of packed red cells that is sustained for at least 2 weeks (from the start date of eltrombopag) or a 50% reduction in the number of units of packed red cells transfused in the 2 consecutive weeks following eltrombopag use compared to the transfusion requirement in the 2 weeks preceding use of the study drug.

**4) Characterization of platelet response to eltrombopag by AML subtype (WHO classification), etiology of AML (*de novo* versus secondary) and cytogenetic risk groups.**

**5) Treatment/Disease outcomes:** CR rates, time to attain CR, CRp rates, time to initiation of post-remission therapy, rates of refractory or persistent disease, survival and safety profile.

Safety will be evaluated from the incidence and severity of adverse events based on clinical assessment and laboratory evaluations, determined according to the Common Terminology Criteria for Adverse Events (CTCAE), version 4.0 of the National Cancer Institute (NCI) Cancer Therapy Evaluation Program (CTEP). Survival will be calculated from the day of study enrollment until the last follow-up or death. Disease-free survival will be calculated from the date of complete remission until relapse, the date of last follow-up, or death.

Response criteria of AML patients to IC will be based on AML International Working Group (IWG) criteria (**Appendix III**). Modified AML response criteria include: morphologic leukemia free state, morphologic CR, cytogenetic CR, molecular CR and CRp. IWG criteria do not require presence of bone marrow cellularity (usually profoundly hypocellular from the effects of cytotoxic chemotherapy) or absence of dysplasia as a criterion for remission status.

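### Appendix III judges platelets for CR only against a baseline and has no CRp row, so incomplete platelet recovery can count as CR and the CRp endpoint has no written criteria

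*Combined protocol and SAP*

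**What the plan says.** The fourth line of outcomes after platelets, bleeding and safety is remission. Section 2.2 sets the objective: "To determine the rates of CR, rates of CRp, time to attain CR, and time to initiation of postremission therapy". Section 10.2, item 5, repeats these as secondary endpoints and adds survival. It says "Response criteria of AML patients to IC will be based on AML International Working Group (IWG) criteria", points to Appendix III, and then names five categories: "Modified AML response criteria include: morphologic leukemia free state, morphologic CR, cytogenetic CR, molecular CR and CRp". It also states "Disease-free survival will be calculated from the date of complete remission until relapse", so the CR date starts that clock.

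Appendix III, as extracted, also has five rows: leukemia-free state, morphologic CR, cytogenetic CR, molecular CR and partial remission. CRp is not among them. Morphologic CR needs marrow blasts under 5%, neutrophils above 1 Gi/L, HI-P and no extramedullary disease. Cytogenetic and molecular CR build on morphologic CR. The partial remission row differs from CR in its blast condition and carries the same HI-P requirement.

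HI-P has two branches. For low starting counts it is "Baseline <20Gi/L: >20 Gi/L and 2x baseline". For a baseline of 20 Gi/L or more it requires at least 50 Gi/L and twice baseline. The extracted text gives no date for the baseline and no transfusion condition. HI-P is followed in the table by the markers 'a b', and no note is labelled with them.

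**The concern.** The case for the drug in AML rests partly on the difference between CR and CRp. Section 1.1 describes "inability to achieve CR, particularly as a result of delayed platelet recovery" as a problem in older patients and reports better long-term survival with CR than with CRp. Section 1.4 lists "improved complete remission rates and timely initiation of post-remission therapy" among the expected benefits of early platelet recovery. For a platelet-raising drug, the platelet component of CR is where an effect on CR would show.

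A purely relative platelet rule works against that. A patient who starts very low can satisfy it with a count that nobody would call recovered, and a patient who starts high can fail it with a normal-looking count. CRp, the category meant to hold remissions without platelet recovery, has no criteria of its own. At stake are the CR rate, the CRp rate, time to CR and disease-free survival.

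**Working it through.** **Is CRp defined anywhere?** Section 10.2 lists five categories ending in CRp. Appendix III prints five rows ending in partial remission. Equal counts make a row lost in extraction unlikely, though not impossible. Section 1.1 expands the abbreviation but gives no criteria. The partial remission row cannot stand in for CRp: it keeps the HI-P condition and changes the blasts, whereas Section 1.1 ties failure to reach CR to platelets.

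**What does HI-P require?** Inputs are the two branches printed in Appendix III. Write b for baseline and x for the later count, both in Gi/L, and read '2x baseline' as at least twice baseline.

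- b < 20: x > 20 and x ≥ 2b
- b ≥ 20: x ≥ 50 and x ≥ 2b

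Lowest whole count that qualifies:

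| Baseline b | 2b | Other limit | Lowest x |
|---|---|---|---|
| 10 | 20 | > 20 | 21 |
| 15 | 30 | > 20 | 30 |
| 19 | 38 | > 20 | 38 |
| 19.9 | 39.8 | > 20 | 40 |
| 20 | 40 | ≥ 50 | 50 |
| 25 | 50 | ≥ 50 | 50 |
| 60 | 120 | ≥ 50 | 120 |
| 150 | 300 | ≥ 50 | 300 |

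Reading '2x' as strictly more than twice would raise some entries by 1 and change nothing of substance.

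**Low end.** Every baseline below 20 qualifies somewhere from 21 to 40. This holds whichever date is taken as baseline. For comparison, the trial's own recovery level in Sections 10.1.1 and 12.0 is 50,000/µL, which is 50 Gi/L.

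**High end, conditional on a pre-induction baseline.** A baseline of 60 needs 120. A baseline of 150 needs 2 × 150 = 300, so 250 fails. Section 8.1 takes a CBC at diagnosis, and the criteria concern response to IC, so pre-induction is the natural reading; the extracted text does not state it.

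**Does the baseline date matter?** Take an assumed patient with 60 at diagnosis and 10 before the first eltrombopag dose. A later count of 45 meets HI-P on the pre-drug baseline (45 > 20 and 45 ≥ 20) and fails on the diagnosis baseline (45 < 120). A count of 110 splits the same way.

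**Transfusion.** Section 4.1 provides for transfusion support. Sections 10.1.2 and 10.2, item 1, write transfusion independence into response to eltrombopag and transfusion-independent platelet recovery. The CR rows as extracted do not.

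**Scale.** The documents give no baseline platelet distribution, so the number reclassified cannot be computed. For orientation only, one patient in 31 is 1/31 = 3.2 percentage points of the CR rate.

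**The case against.** Several stronger conclusions are tempting, and the documents do not support them.

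- *That CR and CRp cannot be told apart.* A reader can infer that CRp is CR without its one platelet condition, and Section 1.1 points that way. The gap is that this is not written, and the inferred boundary would still move with the baseline.
- *That the plan omits a baseline date and a transfusion condition.* The 'a b' markers may belong to a footnote lost in extraction that supplies either. This cannot be settled without the source PDF. A restored footnote would not change the fact that CR rests on a baseline-relative rule.
- *That platelet counts stop once 100,000/µL is reached, so high thresholds could not be observed.* Section 8.2, item 9, continues CBCs per standard of care for 4 weeks after the drug stops or until post-remission therapy, whichever is earlier.
- *That the historical CR rate of 41% has no stated criteria.* Section 10.1.1 refers to IWG criteria when defining that cohort's time to CR. The platelet threshold is not printed, so comparability is open rather than refuted.

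The defence can also say that the appendix is labelled a modification, so HI-P looks deliberate, and that nothing obliges CR to agree with the 50,000/µL recovery endpoint. Both are fair. Naming the baseline and the transfusion handling would remove the ambiguity. It would not stop a rise from 10 to 21 Gi/L from meeting the platelet condition for CR, which sits badly with the rationale in Sections 1.1 and 1.4.

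Finally, these are secondary outcomes, no formal test of CR is planned, and Section 12.0 describes its significance testing as exploratory. That limits the weight of the point without removing it.

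**Conclusion.** The point holds for secondary outcomes and should be corrected. Section 10.2 and Appendix III disagree on whether CRp is a category, and no section gives its criteria. The platelet condition for CR, as printed, admits counts of 21 to 40 Gi/L for every baseline below 20. On a pre-induction baseline, which is an assumption, it also denies CR at 250 to a patient who started at 150.

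CR rate, CRp rate, time to CR and disease-free survival are affected. A reader might infer a sizeable bias in the CR rate; the documents give no basis for a size, because the baseline counts are unknown. The primary endpoint uses an absolute count by day 24, so it, the stopping rule and the sample size are unaffected. Confidence is medium, because the appendix table may be incomplete as extracted.

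**What to change.** 1. Check the source PDF for a CRp row and for notes 'a' and 'b', then reconcile Section 10.2 with Appendix III.
2. Make the platelet condition for CR one absolute, untransfused threshold chosen by the sponsor, and state the transfusion-free window. If CR is to be compared with the historical 41%, match the threshold to the IWG rule applied to that cohort and print that rule.
3. Define CRp as all morphologic CR conditions except that threshold.
4. If HI-P is kept, report it separately as a descriptive measure, with its baseline date and transfusion handling stated.

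The work is wording in the appendix and Section 10.2. Marrow results, CBCs and transfusion dates are already collected under Sections 8.1 to 8.3, so existing records suffice. The cost is in interpretation: the CR rate may fall and the CRp rate rise. For patients already assessed, this redefines an outcome after the data are known in an open single-arm trial. CR should therefore be reported under both the printed and the revised rule, with the date of the change.
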